- Decrease in ejection fraction: Grade ≥ 3 (nadir LVEF $<40-20\%$), related to study drug
- Creatinine elevation: Grade ≥ 3 , related to study drug.
- Any other adverse event of Grade ≥ 3 , related to study drug that in the opinion of the PI is inconsistent with the expected adverse events with standard chemotherapy.

Dose limiting hematologic toxicity is defined by bone marrow and peripheral blood examination at Day ≥ 56 showing:

- Absence of recurrent or persistent leukemia AND
- Persistently hypocellular marrow ($<20\%$ cellularity) AND
- Peripheral blood:
 - ANC < 500 and/or
 - Platelet count $< 10,000$

If more than one dose level is considered acceptably safe, the decision about which one to use for future clinical study will be based on efficacy. Efficacy success for an individual patient is defined as achievement of CR or CRI. Observation of ≤ 3 CR or CRI among 15 patients ($\leq 20\%$) defines a non-efficacious study arm. In situations where both study arms are considered equally safe, the study arm with the higher rate of response will be recommended for future study, provided it equals or exceeds 20%.

When the dose recommended for future study is defined, 10 additional newly diagnosed patients will be treated at that dose level (not to exceed a total of 25 patients at that dose level) to obtain additional evidence of safety and efficacy among previously untreated patients with high risk of induction mortality.

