Treatment success is defined as achievement of CR or CRi. We will accrue a maximum of 15 patients at each dose level and test the null hypothesis that the true response is at most 5% (meaning little or no activity) versus the alternative hypothesis that the true response is 30% or greater, independently in each treatment arm. Assuming that the success rate is binomially distributed, this design with 15 patients in each arm has 87% power and a one-sided type I error rate of 0.05 using an exact test.

To monitor futility, the study in one dose level will be stopped early if the data in that dose level suggest that:

$$\Pr(\theta_E < 0.25 + \theta_s | \text{data}) > 0.95$$

That is, if at any time during the study we determine that there is a greater than 95% chance that the response rate is less likely to improve by 25% than the null hypothesis in one dose level, we will terminate the enrollment in that dose. Here θ_E represents the response rate for experimental drug in this study and θ_s represents the response rate for the standard practice (null hypothesis). We assume that θ_s has a distribution of beta (10, 190) to reflect the information on 200 patients for the historical data, which has a mean response rate of 0.05 and a variance of 0.0002. We also assume that θ_E has a non-informative flat prior beta(0.1, 1.9) with mean of 0.05 and variance of 0.0158.

The futility stopping boundaries for the overall response based on these assumptions and monitoring condition is shown in table 7. For example, accrual will be stopped in one dose if there is no response observed in the first 5 patients treated in that dose.

The toxicity monitoring/efficacy summary will be submitted to the IND Office Medical Monitor ([name]) for every 5 subjects treated in each Arm (per Table 7, 8, 11 & 12).

Table 7: Stopping boundaries for futility monitoring for the initial cohort of each dose (n=15)

# Patients (in complete cohorts of 5) (inclusive)	Stop the enrollment in one dose if there are this many responses total in that dose:

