# Responses (inclusive)	
5	0
10	0-1
15	Always stop with this many patients

Toxicity monitoring

In addition, toxicity will be monitored closely. Denote the probability of toxicity by T_E , where toxicity is defined as DLTs. We assume toxicity rate beta (0.66, 1.34) for the experimental treatment in this study. Our safety monitoring rule is described as follows: $\Pr(T_E > 0.33 | \text{data}) > 0.85$. That is, we will stop the enrollment in one dose if, at any time during the study, we determine that there is more than 85% chance that the DLT rate is more than 33% in that dose. Stopping boundaries corresponding to this stopping rule is listed in table 8. For example, the enrollment in one dose will be stopped if the first 4 of the first 5 patients experienced toxicity in that dose.

Table 8: Stopping boundaries for toxicity monitoring for the initial cohort of each dose (n=15)

# Patients (in complete cohorts of 5) (inclusive)	Stop the enrollment in dose level if there are this many DLTs total in that dose level:

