# DLTs (inclusive)	
5	4-5
10	6-10
15	Always stop with this many patients

The operating characteristics for this design are presented in table 9. If the enrollment in one dose continues until 15 patients are evaluated in each arm and 5 CR or CRi are observed, then the 95% credible interval for the response rate would be (11.6%, 47.7%).

Table 9: Operating characteristics of the initial cohort of each dose (n=15)

True CR+CRi Rate	True DLT Rate	Early Stopping Probabilities	Average sample size treated
0.05	0.1	0.931	6.47
0.05	0.2	0.932	6.46
0.05	0.33	0.938	6.39
0.05	0.5	0.959	6.12
0.1	0.1	0.784	88.13
0.1	0.2	0.787	8.10
0.1	0.33	0.804	7.94
0.1	0.5	0.872	7.30
0.2	0.1	0.462	11.1
0.2	0.2	0.468	11.0
0.2	0.33	0.512	10.66
0.2	0.5	0.681	9.33
0.3	0.1	0.229	13.01
0.3	0.2	0.237	12.95
0.3	0.33	0.30	12.5
0.3	0.5	0.543	10.67
0.3	0.6	0.735	9.08
0.4	0.1	0.098	14.11
0.4	0.2	0.108	14.04
0.4	0.33	0.181	13.50
0.4	0.5	0.465	11.42
0.4	0.6	0.691	9.61

If three dose arms continue until 15 patients in each arm evaluated, the toxicity profile and response will be summarized for them. The dose chosen for further study will be the dose with the highest CR+CRi rate, provided that toxicity profile are also acceptable. The probability of correctly selecting the superior dose for different success rate scenarios in the three arms is summarized in table 10 below [Simon R et al 1985].

Table 10: Probability of the best arm being chosen

True Response rate in Superior Dose	True Response rate in inferior Dose 1	True Response rate in inferior Dose 2	Probability of the best arm is chosen

30%	10%	10%	86%
30%	15%	15%	71%
40%	25%	25%	63%
40%	30%	25%	56%
40%	30%	30%	50%
50%	25%	25%	83%
50%	30%	25%	78%
50%	30%	30%	73%
50%	40%	30%	59%
60%	25%	25%	94%
60%	30%	25%	91%
60%	30%	30%	89%
60%	40%	30%	79%
60%	50%	30%	63%

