The arm with a favorable toxicity profile and/or a favorable might be chosen for further evaluation by expanding a cohort of 10 additional patients in that arm. We will use the same criteria (e.g. expansion will be stopped if $\Pr(T_E > 0.33 | \text{data}) > 0.85$) to monitor toxicity for the expansion cohort by using a total sample size of 25 for the winner arm. The stop boundaries are summarized in the following table. If 10 or more patients out of the 1st 20 patients experienced DLT, the trial will be stopped and no expansion cohort will be evaluated. If 10 or more patients out of 20 patients experienced DLT (by adding 5 more patients to the 15 patients in that arm), the expansion will be stopped.

Table 11. Toxicity monitoring for the expanded cohort at a dose of 75 units/m²

# Patients (in complete cohorts of 5) (inclusive)	Stop the arm with expansion cohort if there are this many dose limiting toxicities total:

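### Section 4.0 makes exactly 3 responses in 15 both a failed arm and an arm that can be recommended, and nothing else in the plan resolves it

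*Combined protocol and SAP*

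**What the plan says.** Two adjacent sentences in Section 4.0 (Study Design) set the efficacy rule for a 15-patient arm.

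- The first takes 3 or fewer "CR or CRI among 15 patients", with 20% or less in brackets, and says that this "defines a non-efficacious study arm".
- The second covers two arms judged equally safe: "the study arm with the higher rate of response will be recommended for future study, provided it equals or exceeds 20" percent.

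Section 4.0 then assigns 10 further patients to whichever dose is recommended.

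Three parts of Section 10.0 bear on the same decision.

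- The power statement, for a null of 5% against 30%: "this design with 15 patients in each arm has 87% power and a one-sided type I error rate of 0.05 using an exact test". No critical value is printed.
- The Bayesian futility rule, with a 0.95 limit. Table 7 gives its boundaries at 5 patients (0 responses) and 10 patients (0-1). At 15 patients the entry is "Always stop with this many patients".
- The selection rule after the 15-patient arms are complete: "The dose chosen for further study will be the dose with the highest CR+CRi rate, provided that toxicity profile are also acceptable". It contains no minimum response rate.

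**The concern.** The count and the percentage in the first sentence agree with each other (3/15 = 20%), so the first rule fails an arm at exactly 20%. The second rule lets an arm through at exactly 20%. At 2 or fewer and at 4 or more the sentences agree; only 3/15 is caught between them.

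CR/CRi is the primary endpoint and the trial is open-label. If the better arm finished at 3/15, Section 4.0 could be cited for calling it non-efficacious or for recommending it, and the choice could be made after the data were seen. How much this matters depends on how likely that count is and on whether Section 10.0 supplies the missing answer.

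**Working it through.** **Inputs.** n = 15 per arm, null 5%, alternative 30%, one-sided 0.05, exact test, stated power 87% (Section 10.0, Futility monitoring). Futility limit 0.95 with priors beta(10, 190) for the standard rate and beta(0.1, 1.9) for the experimental rate (same place). Stops at 0 of 5 and at 0-1 of 10 (Table 7).

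**1. The plan's own power figure.** With X binomial(15, p) and success declared at X ≥ r:

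| r | P(X ≥ r) at 5% | P(X ≥ r) at 30% |
|---|---|---|
| 2 | 0.171 | 0.965 |
| 3 | 0.0362 | 0.873 |
| 4 | 0.0055 | 0.703 |

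Only r = 3 keeps the error at or below 0.05 and gives 87%. The stated power reproduces, and 3/15 rejects the 5% null.

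**2. The futility formula.** The quantity is Pr(θ_E < 0.25 + θ_S | data), with θ_S ~ beta(10, 190) and θ_E ~ beta(0.1 + x, 1.9 + n − x) after x responses in n, by numerical integration.

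- n = 5: 0.996 at x = 0 (stop), 0.858 at x = 1 (continue). Matches Table 7.
- n = 10: 0.975 at x = 1 (stop), 0.870 at x = 2 (continue). Matches Table 7.
- n = 15: 0.968 at x = 2 (above 0.95), 0.887 at x = 3 (below 0.95), 0.733 at x = 4.

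By this formula 3/15 is not futile. Table 12, with its looser 0.98 limit, stops at 0-1 of 15, so 3/15 continues there too.

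**3. How often an arm ends at exactly 3/15.** Let a, c and e be the responses in successive groups of five. An arm reaches 15 only if a ≥ 1 and a + c ≥ 2. The arrangements with three responses that survive are (1,1,1) 125, (1,2,0) 50, (2,0,1) 50, (2,1,0) 50 and (3,0,0) 10, in total 285. Hence P(exactly 3) = 285 p³(1 − p)¹²:

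- p = 0.20: 0.157
- p = 0.30: 0.107
- p = 0.40: 0.040

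Check on the stopping part at p = 0.30: 0.7⁵ + 5(0.3)(0.7⁴)(0.7⁵) = 0.1681 + 0.0605 = 0.2286. Table 9 gives 0.229 at a DLT rate of 0.1, where toxicity stops add almost nothing.

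**4. Passing probability at p = 0.30 with the futility stops.** Surviving arms with exactly two responses number 25 + 10 = 35 arrangements, so P(exactly 2) = 35(0.3²)(0.7¹³) = 0.0305. Then P(≥ 3) = 1 − 0.2286 − 0.0305 = 0.741, and P(≥ 4) = 0.741 − 0.107 = 0.634. The same steps give P(≥ 3) = 0.461 at p = 0.20 and 0.895 at p = 0.40.

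**5. One arm strictly better at exactly 3/15.** The recommendation sentence needs an arm with the higher rate, so 3-3 ties are excluded. For independent arms A and B the probability is P(A = 3)·[1 − P(B ≥ 3)] + P(B = 3)·[1 − P(A ≥ 3)], where a futility-stopped arm counts as below 3:

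- 20%/20%: 2 × 0.1567 × 0.5389 = 16.9%
- 30%/20%: 0.1065 × 0.5389 + 0.1567 × 0.2591 = 9.8%
- 30%/30%: 2 × 0.1065 × 0.2591 = 5.5%
- 40%/30%: 0.0397 × 0.2591 + 0.1065 × 0.1052 = 2.1%

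**The case against.** The strongest reply is that Section 10.0 does not adjudicate. Its exact test asks whether the rate exceeds 5%, and its futility rule decides whether enrolment goes on. Neither defines what is good enough to recommend, and a plan may demand more for a recommendation than rejecting 5%. A posterior of 0.887 at 3/15 is also weak praise: it is an 89% probability that the arm falls short of the targeted 25-point gain. This stands. A reader might infer that the failure rule of 3 or fewer is the mistaken sentence, or that the 87% power is wrong. The documents support neither: the slip could lie in either sentence, and 87% is correct for the test against 5%.

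A reader might also think Table 7 lacks a boundary at 15. It governs enrolment, and enrolment of the initial cohort ends at 15, so no row is missing. Nor does the cut-off dictate how each arm is reported. The Statistical methods text in Section 10.0 calls for rates with 95% confidence intervals and a Fisher comparison, without a pass/fail label.

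Finally, the selection may be past. Section 4.0 says that 100 units/m² was found safe and adds 25 patients there without reference to this cut-off, and Table 11 is titled "Toxicity monitoring for the expanded cohort at a dose of 75 units/m²". That suggests, but does not prove, that the 15-patient comparison had been made. None of this removes the clash between the two sentences.

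**Conclusion.** The contradiction is real and confined to Section 4.0: at exactly 3/15 the plan gives opposite answers on the primary endpoint. Section 10.0 does not set the recommendation floor, though 3/15 passes both of its criteria.

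The count is plausible, at 4% to 16% for a single arm over true rates of 40% down to 20%, and 2% to 17% for one arm being strictly the better of two. Whether 3/15 counts as a pass moves the chance of clearing the floor at a true 30% from 70.3% to 87.3% single-stage, or from 63.4% to 74.1% with the futility stops.

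These probabilities assume independent binomial arms and Table 7 applied exactly as printed. They ignore toxicity stops, the equal-safety condition and any third arm. The reach is one count in equally safe arms, and the 100 units/m² expansion does not depend on it. It should be fixed, but it does not undermine the design.

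**What to change.** State one 15-patient efficacy cut-off in Section 4.0. Either version is coherent:

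- Define non-efficacious as 2 or fewer of 15 (below 20%) and leave the recommendation floor at 20% or more. This matches the critical value behind the stated 87% power.
- Keep 3 or fewer of 15 as non-efficacious and change the recommendation floor to more than 20%. Add that the chance of clearing this floor at a true rate of 30% is 70% single-stage (63% with the Table 7 futility stops), and that 87% applies only to the test against 5%.

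If the 15-patient results are already known, record that the wording was settled after those data and whether any arm ended at 3/15.

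The cost is one changed sentence, plus a short power note under the second option. No patients are added, and no stopping boundary or table changes.

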4.1 Patient Recruitment

All patients will be screened by a principal investigator or sub-investigator prior to entry on the study. An explanation of the study and discussion of the expected risks and benefits will be fully discussed with patients prior to the screening process in order for the patient to provide a voluntary written informed consent. Only eligible and consenting patients will be entered into the study.

4.2 Registration Procedures

Patients will be registered through CORe.

4.3 Patient Sample Size

A maximum of 80 patients will be treated.

A minimum of 15 patients will be treated at each dose level, unless conditions for early stopping are met based on excessive toxicity or insufficient safety (see section 10.0).

4.4 Toxicity Assessment

Toxicities will be evaluated and graded according to the NCI Common Terminology Criteria for Adverse Events, version 4 (CTCAE).

If a patient is discontinued due to progressive disease or intercurrent illness unrelated to toxicity attributable to CPX-351 and before safety can be assessed to rule out DLT, an additional patient will be recruited, to ensure that the minimum number of patients are evaluable for safety at each dose level.

4.5 Second Inductions

A second induction may be given if:

- The first induction does not produce a day 28 bone marrow demonstrating morphologic leukemia free state ($\leq 5\%$ blasts)
- Second inductions are given at the discretion of the investigator but are recommended in any patient with documentation of reduced leukemic burden, especially those with evidence of partial remission ($\geq 50\%$ reduction in % blasts count to 5-25% blasts).
- Second induction may be started on Day 28 from 1st cycle. In patients with rapidly proliferating disease second induction may be started earlier (but not earlier than Day 21) provided there is no residual study drug-related grade 2 non-hematologic toxicity after discussion with the principal investigator.

The CPX-351 dose for second induction is the same as for initial induction except that doses are given on Days 1 and 3 only. Patients unable to achieve a response (CR+CRi) after two inductions are discontinued from further treatment and are followed for survival only.

4.6 Consolidation Therapy

Only patients with documented response (CR or CRi) are eligible for consolidation. Consolidation with stem cell transplant (HSCT) is permitted either in place of chemotherapy consolidation or after chemotherapy consolidation. Prior to beginning every other chemotherapy consolidation after the cumulative DNR dose exceeds 300 mg/m², or prior to every course of treatment after the cumulative DNR dose exceeds 500 mg/m², patient LVEF must be documented to be $\geq 50\%$ and patient PS must be 0-2.

Patients in CR with full recovery of peripheral blood counts within 56 days may be consolidated starting within one week of documentation of response. Patients with CRi may start consolidation no earlier than 42 days after the start of the last induction course

and only if ANC is $>500/\mu\text{L}$ and Platelets are $>50,000/\mu\text{L}$. Consolidation courses consist of 2 doses administered at 65 units/ m^2 on days 1 and 3.

A maximum of 4 courses of consolidation will be administered. It is understood that variations in timing of second induction and consolidations may be necessary and will be decided on a case by case basis by the PI. The rationale for variations in schedule will be documented by the PI. If consolidation is well tolerated and hematopoietic recovery is not delayed beyond 56 days, additional courses of consolidation may be offered immediately at time of recovery. In cases of poor patient tolerance or delayed hematopoietic recovery, the principal investigator will document his decision to either continue or terminate consolidation treatment.

Consolidation dosing:

First Consolidation	
Induction Outcome	Consolidation Dose
CR after induction ≤ 56 days	May start within one week of documentation of CR
CR after >56 days	Delay start of consolidation until day 70
CRi with at least ANC to $\geq 500/\mu\text{L}$ and platelets to $\geq 50,000/\mu\text{L}$	Starts after day 42.
CRi with ANC $<500/\mu\text{L}$ or platelets $<50,000/\mu\text{L}$	No consolidation to be given
Second and Subsequent Consolidations	
Previous Consolidation Outcome	Consolidation Dose
Count recovery to pre-consolidation baseline by Day 56	Same as first consolidation
Partial count recovery ANC ($\geq 500/\mu\text{L}$ and platelets to $\geq 50,000/\mu\text{L}$ by Day 56)	Delay second induction until day 70
Failure to recover (ANC $<500/\mu\text{L}$ or platelets to $<50,000/\mu\text{L}$) by Day 56	No consolidation to be given

Variations of the schedule mentioned above may be considered in individual patients if felt to be in the best interest of the patient after discussion with the principal investigator and with proper documentation of the rationale for the change.

4.7 Salvage Therapy

Patients who never achieve CR/CRi following initial induction and patients who achieve CR/CRi and later relapse may receive salvage therapy.

4.8 Patient Follow-up

Follow-up for CR duration, EFS and safety (if applicable) terminates at the time of relapse, start of salvage or non-protocol treatment for leukemia (for persistent disease or transplant conditioning chemotherapy).

4.9 Study Modification/Discontinuation

Any amendments to the study will be documented in a revised protocol with a new assigned version.

The Investigator and the IND Office may stop the trial early for the following reasons:

- Unacceptable toxicity
- Discontinuation of drug development
- Poor enrollment
- Request by a regulatory authority

In the case of study discontinuation, the principal investigator will notify and discontinue patients from the trial and inform the IRB.

5.0 Selection and Withdrawal of Patients

5.1 Study Population

5.1.1 *Inclusion criteria*

- 5.1.1.1 Ability to understand and voluntarily sign an informed consent form
- 5.1.1.2 Age ≥ 18 years at the time of diagnosis of AML
- 5.1.1.3 Pathological diagnosis of AML according to WHO criteria (with at least 20% blasts in the peripheral blood or bone marrow):
 - Newly Diagnosed De novo AML; except for APL
 - Newly Diagnosed Secondary AML, defined as having a history of an antecedent hematologic disorder (myelodysplastic syndromes [MDS], myeloproliferative disease [MPD] or history of cytotoxic treatment for non-hematologic malignancy) or apparent de novo AML with MDS-associated karyotype. (Appendix 9)
- 5.1.1.4 Eastern Cooperative Oncology Group (ECOG) performance status 0-3
- 5.1.1.5 Laboratory values fulfilling the following:
 - Serum creatinine ≤ 2.0 mg/dL
 - Serum total bilirubin ≤ 2.0 mg/dL
 - Serum alanine aminotransferase < 3 times the ULN Note: If elevated liver enzymes are related to disease ALT should be < 5 times ULN.
- 5.1.1.6 To be considered at high risk for induction mortality patients must have 1 or 2 of the following risk factors (patients ≥ 60 must have at least 1 risk factor, patients < 60 must have at least 2 risk factors) present. At least one risk factor in every patient must be an AML-related factor:
AML-related factors include:
 - AHD (MDS, CMML, or MPD) or history of exposure to cytotoxic chemotherapy (t-AML), or WHO-defined AML with MDS-related changes or apparent de novo AML with MDS-associated karyotype.
 - Unfavorable cytogenetics as defined by the European Leukemia Net (Appendix F) Appendix 11

Patient-related factors:

- Age ≥ 70
- ECOG PS ≥ 2
- Co-morbidities: Serum creatinine >1.3 g/dL

5.1.1.7 Cardiac ejection fraction $\geq 50\%$ by echocardiography or MUGA (when LVEF expressed as a range, at least the upper limit should include 50%).

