For patients with older age or co-morbidities the risk of induction treatment remains high. Patients age 65 or older treated with standard 3+7-like chemotherapy have been reported to have an induction mortality rate of 20%.(8, 10) Those with adverse cytogenetic abnormalities have a significantly higher risk of early mortality.(8, 11) At MD Anderson, patients at relatively high (30-50%) risk for induction mortality (60-day) can be identified. Patients in this age group with adverse cytogenetic abnormalities have an early mortality rate of 35% compared to 22% for those in the same age group with diploid cytogenetics (Tambaro et al. ASH 2012). In addition, an analysis of 998 patients age 65 or older with AML or high-risk MDS analyzed the factors associated with increased risk for early mortality and, consequently, poor long-term outcome. By multivariate analysis, age 75 years or older, performance status ≥ 2 , complex karyotype, treatment outside a laminar air-flow setting, antecedent hematologic disorder of at least 12 months duration prior to the diagnosis of AML, and a creatinine $>1.3 \text{ mg/dL}$ were identified as independent factors associated with increased risk of mortality by 8-weeks from the start of induction chemotherapy.⁽³⁾ Patients with none of these risk factors have an 8-week mortality probability of 10%, with a median survival of 16 months and 1-year projected survival of 58% and are considered a low-risk group. In contrast, for those with 1 or 2 risk factors (i.e., the intermediate risk group) the 8-week mortality rate is 19-36% with median survival of 4-9 months and 1-year survival rates of 22-35%. Those with 3 or more risk factors (the high-risk group) have a 65% probability of early mortality, median survival of 1 month and 1 year projected survival of 8%.⁽³⁾ For patients with intermediate or high risk the decision to treat with intensive chemotherapy is difficult because the benefits have been approximately equal to the risks. Studies using non-intensive treatment have been performed indicating reduced early risk with reduced benefit. The need for effective treatment with acceptable treatment safety remains urgent.

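### The creatinine risk factor in 5.1.1.6 is given in g/dL and cannot be met under the 2.0 mg/dL entry limit; taken literally, it wrongly excludes a narrow group under 60

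*Combined protocol and SAP*

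**What the plan says.** Three places in the combined protocol and SAP give a creatinine threshold.

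- Section 5.1.1.6, patient-related risk factors: "Co-morbidities: Serum creatinine >1.3 g/dL".
- Section 5.1.1.5, laboratory values required for entry: "Serum creatinine ≤ 2.0 mg/dL".
- Section 2.1, background, on an analysis of 998 patients aged 65 or older: "a creatinine $>1.3 \text{ mg/dL}$ were identified as independent factors associated with increased risk of mortality by 8-weeks".

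The counting rule is also in 5.1.1.6. It opens with "patients must have 1 or 2 of the following risk factors", then sets the number by age: "patients ≥ 60 must have at least 1 risk factor, patients < 60 must have at least 2 risk factors". It adds: "At least one risk factor in every patient must be an AML-related factor".

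The list has five entries. Two are AML-related: antecedent disorder, therapy-related or MDS-type disease; and unfavorable ELN cytogenetics. Three are patient-related: age 70 or over, ECOG performance status 2 or worse, and creatinine. No other section corrects or explains the g/dL unit.

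**The concern.** This line is an operative entry criterion, not background text. Creatinine is the only co-morbidity or organ-function item in the list, although Section 4.0 names both kinds of factor as contributors to risk. If the line is applied as printed, that item can never be counted.

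A patient under 60 needs two factors and cannot have the age factor. With creatinine void, poor performance status is the only patient-related factor left to such a patient. Someone with one AML-related factor, good performance status and moderately raised creatinine would then be turned away. If staff instead read the unit as mg/dL without saying so, that patient is enrolled on a criterion the approved text does not contain.

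**Working it through.** **1. Units.** The inputs are the two thresholds in Section 5.1 and the one in Section 2.1.

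- 1.3 g/dL × 1,000 mg/g = 1,300 mg/dL.
- Against the entry limit: 1,300 / 2.0 = 650.
- Against Section 2.1: 1,300 / 1.3 = 1,000.
- Range that meets both criteria as printed: above 1,300 and at most 2.0 mg/dL, which is empty.
- Range with the unit of Section 2.1: above 1.3 and at most 2.0 mg/dL, which is not empty.

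**2. Counting rule.** Let *a* be the number of AML-related factors (0, 1 or 2), *g* = 1 if age is 70 or over, *p* = 1 if performance status is 2 or worse, and *c* = 1 if the creatinine factor counts. Then *n* = *a* + *g* + *p* + *c*. A patient qualifies if *a* ≥ 1 and *n* ≥ 2 (under 60) or *n* ≥ 1 (60 or over). For a patient with creatinine above 1.3 and up to 2.0 mg/dL, *c* = 0 as printed and *c* = 1 in mg/dL.

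There are 24 profiles: three age bands (under 60, 60-69, 70 or over) times the eight combinations of the two AML-related factors and performance status. Profiles are not weighted by how common they are.

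**3. Required number read as a minimum, no cap.** Two of the 24 profiles change. Both are under 60, with *a* = 1 (either AML-related factor alone) and *p* = 0. As printed *n* = 1, not eligible; in mg/dL *n* = 2, eligible. At 60 or over the mandatory AML-related factor already gives *n* ≥ 1, so nothing changes.

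**4. '1 or 2' read as a maximum (*n* ≤ 2 also required).** Ten of the 24 profiles change.

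| Age | a | p | n as printed | n in mg/dL | Eligibility | Profiles |
|---|---|---|---|---|---|---|
| <60 | 1 | 0 | 1 | 2 | no → yes | 2 |
| <60 | 1 | 1 | 2 | 3 | yes → no | 2 |
| <60 | 2 | 0 | 2 | 3 | yes → no | 1 |
| 60-69 | 1 | 1 | 2 | 3 | yes → no | 2 |
| 60-69 | 2 | 0 | 2 | 3 | yes → no | 1 |
| ≥70 | 1 | 0 | 2 | 3 | yes → no | 2 |

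Under this reading the printed unit keeps out two profiles and lets in eight.

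**5. Design figures.** The stated 87% power in Section 10.0 is reproduced with 15 patients, response rates of 5% and 30%, and success at 3 or more responses: power 0.873, exact type I error 0.036. Creatinine is not an input. The stopping rules use only response and DLT counts, and the planned comparisons do not use creatinine or a factor count.

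**The case against.** The strongest reply is that this is an obvious slip. No patient has a creatinine of 1,300 mg/dL, mg/dL is printed a few lines earlier, and Section 2.1 carries the same number in mg/dL. Most screening staff would probably read it that way, and the documents give no sign that anyone applied the line literally. That stands and limits the severity. It does not remove the point, because an entry criterion should not depend on readers departing from its text.

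The affected group may be narrower still. Complex karyotype, –7 and –5 or del(5q) appear both in the MDS-associated list (Appendix 9) and in the ELN adverse list (Appendix 10). If the two AML-related entries are counted separately, those patients already have two factors. The protocol does not say whether they are.

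A reader might infer more than the documents support:

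- *A route to entry is lost for everyone with raised creatinine.* Creatinine can never qualify a patient alone in either unit, because an AML-related factor is mandatory.
- *The ratios of 1,000 and 650 measure the harm.* They measure the slip; for most patients in the range eligibility is the same (without a cap).
- *A recorded factor count is wrong throughout.* Section 6.1 asks only for the reason a patient was judged high risk. It prescribes no count and no check against a maximum.
- *The risk model in Section 2.1 proves the factor matters in younger patients.* That analysis covered patients aged 65 or older. Its list also differs from 5.1.1.6: age 75 rather than 70, and an antecedent disorder of at least 12 months rather than any duration. It supports the unit, not a claim about patients under 60.

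**Conclusion.** The point holds in limited form. As printed, the creatinine factor cannot be met by any patient who satisfies 5.1.1.5. That the intended unit is mg/dL is an inference, but both other thresholds in the document support it.

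On the minimum reading, literal use wrongly excludes one kind of patient: under 60, exactly one AML-related factor, performance status 0-1, creatinine above 1.3 and up to 2.0 mg/dL. Eligibility at 60 or over changes only if the phrase 1 or 2 is a cap. The age-specific wording, which sets minimum numbers, argues against a cap, but the text does not settle it. The documents do not say how many screened patients fall in either group, so the number affected cannot be estimated.

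This is a worthwhile correction to an eligibility line. It gives no reason to doubt the sample size, power, monitoring boundaries or planned analyses.

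**What to change.** 1. Reconcile the unit in 5.1.1.6 with 5.1.1.5 and Section 2.1, and issue it as a revised protocol version as Section 4.9 requires. The document's own figures point to mg/dL.
2. In the same revision, state whether the phrase 1 or 2 is a maximum or only a summary of the age-specific minimum. This decides how far the unit matters.
3. Check screening decisions for patients under 60 with creatinine above 1.3 and up to 2.0 mg/dL, and record which unit was applied. If a maximum of two was intended, extend the check to all ages and include enrolled patients.

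The cost is one unit, one clarifying sentence and a short record check. Creatinine is already measured within one day before registration, and Section 6.1 requires screening to be noted in the source documents. No reanalysis or redesign is needed.
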